STATISTICAL ANALYSIS PLAN

A pragmatic cluster randomised controlled trial of the 'Fostering Connections' programme: Examining the impact of trauma-informed training and support for social workers on youth in care in family settings

Centre for Evidence and Implementation and Bryson Purdon Social Research

Principal investigator: [name]

A pragmatic cluster randomised controlled trial of the 'Fostering Connections' programme: Examining the impact of trauma-informed training and support for social workers on youth in care in family settings

Statistical analysis plan

Evaluating institution: Centre for Evidence and Implementation and Bryson Purdon Social Research
Principal investigator(s): [name]

Project title	A pragmatic cluster randomised controlled trial of the 'Fostering Connections' programme: Examining the impact of trauma-informed training and support for social workers on young people in care in family settings
Developer (Institution)	National Children's Bureau
Evaluators (Institutions)	Centre for Evidence and Implementation and Bryson Purdon Social Research
Principal investigator(s)	[name]
SAP author	[name], BPSR
Trial design	Two-armed cluster randomised controlled trial with random allocation at the level of the young person's social worker
Trial type	Efficacy
Evaluation setting	Family and children's services settings

Target group	Young people in care in foster care or supported lodgings, aged 10-17 years old
Number of participants	558 young people at baseline; 391 young people at follow-up
Primary outcome and data source	Young person outcome: Externalising behaviour measured through the Strength and Difficulties Questionnaire (carer report version, externalising score)
Secondary outcomes and data sources	
Young person outcomes:
 
 1. Internalising score of the Strength and Difficulties Questionnaire (carer report version, internalising score) 2. Prosocial subscale of the Strength and Difficulties Questionnaire (carer report version) 3. Involvement with criminal justice system measured through conviction or subject to youth caution (SSDA903) 4. Transition into residential care (SSDA903) 5. Placement stability measured through unplanned moves (SSDA903) 6. Missing from care (SSDA903) 
Foster carer outcomes:
 
 7. Compassion satisfaction reported by foster carers, measured through the Professional Quality of Life (ProQOL) scale (self-report) 8. Burnout reported by foster carers, measured through the ProQOL scale (self-report) 9. Secondary traumatic stress reported by foster carers, measured through the ProQOL scale (self-report)

	
10. Trauma-informed knowledge reported by foster carers, measured through a bespoke questionnaire (self-report)
 
Supervising social worker and young person’s social worker outcomes:
 
11. Attitudes to trauma-informed practice reported by social workers, measured through the Attitudes Related to Trauma-Informed Care (ARTIC) scale

--	--

SAP version history

Version	Date	Changes made and reason for revision
1.2 [latest]		
1.1		
1.0 [original]		[leave blank for the original version]

Any changes to the design or methods need to be discussed with the YEF Evaluation Manager and the developer team prior to any change(s) being finalised. Describe in the table above any agreed changes made to the evaluation design. Please ensure that these changes are also reflected in the SAP (CONSORT 3b, 6b).

Table of contents

SAP version history	3
Table of contents	4
Introduction	5
Design overview	7
Sample size calculations overview	11
Analysis	15

Introduction

The National Children's Bureau (NCB) and Leap Confronting Conflict (Leap CC) have partnered to deliver the 'Fostering Connections' training programme for young person social workers (YPSWs) and supervising social workers (SSWs), aimed at enabling young people (YP) aged 10-17 years old in foster care or supported lodgings to have reduced emotional and behavioural difficulties, including through the strengthening of meaningful relationships with trusted adults. To do so, the training seeks to improve professional relationships and communication between young people's social workers (YPSWs) and supervising social workers (SSWs), improve support for foster carers (FCs) (including kinship/connected carers and host families of young people aged 16 and 17 in supported lodgings), and increase understanding of trauma and implementation of trauma informed practice from the adults supporting YP in care (FCs, SSWs and YPSWs).

The trial is being run in eight LAs across England.

YPSWs and SSWs assigned to the intervention arm of the trial will be offered the training. They will be provided with an e-learning module (around 45 min), 7 days of face to face training and 3 days of reflective practice over five months, followed by monthly cross-LA virtual follow-up workshops and an online peer support network. Trained staff work with the young person and/or their FC across the 10 to 12-month period from start of the training to follow-up (including after the intervention ends).

The trial aims to address a broad range of research questions:

The **primary** question to be addressed by the trial is:

Research Question 1 (RQ1): What is the impact of providing the training and support to both YPSWs and SSWs on the externalising behaviour of YP in care in family settings? This will be measured using the Strengths and Difficulties Questionnaire (SDQ), completed by FCs/supported lodgings providers at baseline and follow-up.

Secondary research questions focus on wider impacts on YP, as well as on impacts on SSWs, YPSWs and FCs. These ask questions about the impact of providing training and support to YPSWs and SSWs on:

Young people

RQ2: What is the impact of providing the training and support to both YPSWs and SSWs on the stability of foster care/supported lodging placements for YP, measured using

SSDA903 data¹ on reasons for moves (those categorised as ‘unplanned’) and transitions into residential care?

RQ3: What is the impact of providing the training and support to both YPSWs and SSWs on YP’s involvement with the criminal justice system, measured using youth cautions and convictions data in the SSDA903?

RQ4: What is the impact of providing the training and support to both YPSWs and SSWs on YP’s episodes missing from care² as reported in the SSDA903?

RQ5: What is the impact of providing the training and support to both YPSWs and SSWs on the internalising and prosocial subscales of the SDQ, completed by FCs/supported lodgings providers at baseline and follow-up.

YPSWs and SSWs

RQ6: What is the impact of providing the training and support to both YPSWs and SSWs on their attitudes towards TIP, measured using the ARTIC scale?

Foster carers

RQ7: What is the impact of providing the training and support to both YPSWs and SSWs on the compassion satisfaction, burnout, and secondary traumatic stress of FCs/caregivers in a family setting, measured using the ProQOL?

RQ8: What is the impact of providing the training and support to both YPSWs and SSWs on the FCs’ attitudes towards TIP, measured using a bespoke questionnaire that builds upon other TIP surveys.

Although the intervention is being delivered to YPSWs and SSWs, the trial primarily focuses on the measurement of the impact of the intervention on eligible YP. For a YP to be in scope for the trial, the young person needs to meet the basic age criteria (10-17), but also needs to have both a YPSW and SSW that is in-scope for the trial. If some YPSWs or SSWs are excluded from the trial (which can, for example, happen if Independent Fostering Agencies (IFAs) are excluded in some LAs) then the YP they are assigned to is not included in the trial.

Within each LA, the YPSWs and SSWs eligible for the trial are:

¹ That is, administrative data that is collected via the ‘Children looked after return’.

² Missing from care: a looked-after child who is not at their placement or the place they are expected to be (for example school) and their whereabouts is not known.

1. YPSWs whose caseload includes at least one young person aged 10 to 17 at the start of the trial;
2. SSWs working with a FC or supported lodgings provider with an eligible YP in their care at the start of the trial.

Design overview

The trial is being run as a two-arm cluster randomised controlled trial with random allocation at the level of the YPSW. Each SSWs is assigned to the same group as the YPSW with which they work most frequently. The unit of analysis for the primary outcome is the YP. As is explained in more detail in the randomisation section, **the randomisation leads to a trial with four arms as follows, but only the first two of the arms are to be used in the main trial analysis**³: (i) YP where both the YPSW and SSW are assigned to the training; (ii) YP where neither the YPSW nor the SSW are assigned to the training; and (iii) YP where the YPSW is assigned to the training but the SSW is not; and (iv) YP where the SSW is assigned to the training but the YPSW is not. This document focuses on the main trial analysis of the first two arms. Analysis that incorporates all four arms is described in the final section of this document 'Analysis of all four arms of the trial'.

Data collection

Data for the trial is being collected at two points in time, at baseline (prior to randomisation of the YPSWs) and at a follow-up point 10 to 12 months later, via online surveys directed at the in-scope YPSWs and SSWs, and FCs. The SDQ data for YP is being collected via the online surveys sent to the FCs. Social Worker involvement in the trial is not dependent on FCs agreeing to complete the surveys, so there is inevitably a fairly high percentage of missing data for YPs and FCs at both baseline and follow-up. Likewise, social workers are randomised to intervention or control irrespective of whether they complete a baseline or follow-up questionnaire.

FCs will be asked to complete a follow-up questionnaire to cover their own outcomes even if their eligible YP is no longer in their care. In cases where a YP moves to another FC, the new FC will be asked to complete the SDQ at follow-up. If a YP moves out of foster care entirely they will be excluded from the trial analysis, the exception being the secondary outcomes that capture moves. Social workers will be asked to complete follow-up questionnaires even if they have changed jobs, but we expect the response rate for movers to be low.

³ As is described later in the randomisation section, this is because the four arms are not all equivalent, with the first and second arms being balanced, and the third and fourth, but without balance across between the first/second and third/fourth arms.

Four secondary outcomes for YP are making use of standard administrative data collected for the SSDA903. We expect to have close to complete data on these outcomes for all YP who stay in foster care.

Table 1: Trial design

Trial design, including number of arms		Two-armed cluster randomised controlled trial
Unit of randomisation		Young person’s social worker (YPSW)
Stratification variables (if applicable)		Local Authority (LA)
Primary outcome	variable	Young person’s externalising behaviour
	measure (instrument, scale, source)	Externalising score, Strengths and Difficulties Questionnaire (Goodman, Meltzer & Bailey, 1998), carer-reported version, fielded in online survey 10-12 months after baseline
Secondary outcome(s)	variable(s)	Young person: SDQ Internalising and Prosocial sub-scales; Involvement with criminal justice system; transition into residential care, placement stability; missing from care episodes SSW / YPSW: Attitudes to trauma-informed practice FCs: compassion satisfaction, burnout; secondary traumatic stress; attitudes to trauma-informed practice
	measure(s) (instrument, scale, source)	Young person: SDQ, carer-report version; Child conviction or subject to youth caution (SSDA903 2024-25); transition into residential care (SSDA903 2024-25); unplanned moves (SSDA903 2024-25); missing from care episodes (SSDA9035 2024-25). SSW / YPSW: ARTIC scale at 12 month after baseline FCs: Professional Quality of Life Scale (self-report), bespoke questionnaire (self-report) at 10-12 months after baseline
Baseline for primary outcome	variable	Young person’s externalising behaviour
	measure (instrument, scale, source)	Externalising score, Strengths and Difficulties Questionnaire, carer-report (Goodman et al, 1998), fielded in online survey as close as possible to randomisation of YPSW

Baseline for secondary outcome	variable	
Young person: Emotional and behavioural difficulties; Involvement with criminal justice system; Transition into residential care, placement stability; missing from care episodes
 
SSW / YPSW: Attitudes to trauma-informed practice
 
FCs: compassion satisfaction; burnout; secondary traumatic stress; attitudes to trauma-informed practice

	measure (instrument, scale, source)	
Young person: SDQ, carer-report version; Child conviction or subject to youth caution (SSDA903 2023-2024); transition into residential care (SSDA903 2023-2024); unplanned moves (SSDA903 2023-2024); missing from care episodes (SSDA903 2023-2024)
 
SSW / YPSW: ARTIC Scale prior to randomisation
 
FCs: Professional Quality of Life Scale (self-report); bespoke questionnaire (self-report) as close as possible to randomisation of YPSW

Randomisation

There are constraints on the number of training places per LA⁴, so YPSWs per LA have not typically been allocated to intervention and control group in the ratio 50:50. Instead, the percentage allocated to the intervention was set so that all available places were filled, with up to a maximum of 70% being allocated to the intervention. In practice, for most LAs, the percentage allocated to the intervention was around 46%. Randomisation was run separately per LA by the trial statistician, giving implicit stratification by LA. Since the trial statistician is undertaking the randomisation and will conduct the statistical analysis, the analysis will not be blind to allocation.

A significant complication in this trial is that the primary analysis aims to test whether delivering the intervention to both SSWs and YPSWs improves outcomes for YP, rather than simply testing whether delivering the intervention to one set of professionals or the other has an impact. Yet, SSWs do not cluster within YPSWs (or vice versa), so straightforward randomisation of YPSW/SSW pairs is not feasible. Inevitably some young people in each LA will have a SSW who has been assigned to the intervention group and a YPSW who has been assigned to the control group, and vice versa. That is, when the randomisation is complete, there will be YP in each of four arms, with the first two (in bold) being the primary analysis arms:

⁴ Depending on the number of in-scope social workers in an LA, either one or two training groups were allocated to the LA, with the maximum number of places per group being 35.

Arm 1: T_{SSW}T_{YPSW} (i.e. both SSW and YPSW assigned to the intervention);

Arm 2: C_{SSW}C_{YPSW} (i.e. both SSW and YPSW assigned to the control group);

Arm 3: T_{SSW}C_{YPSW} (i.e. SSW assigned to the intervention and YPSW assigned to the control group);

Arm 4: C_{SSW}T_{YPSW} (i.e. SSW assigned to the control group and YPSW assigned to the intervention group).

As noted, the primary trial analysis will focus on YP within ‘Analysis Arms’ 1 and 2 (that is, pure intervention and pure control). Young people in Arms 3 and 4 will be excluded from the primary analysis. Arms 3 and 4 will however be included in an exploratory analysis, where the impact of just one of the two YPSWs/SSWs being assigned to the intervention is estimated. This is described in the final section ‘Analysis of all four arms of the trial’.

The randomisation method aims to maximise the sample size for the primary analysis. Each SSW was assigned to a ‘unique YPSW’ prior to the start of the trial, with this being done by assigning each SSW to the YPSW with whom they share the most eligible YP. To illustrate, if a SSW has 10 eligible YP, and for five of the 10 they work alongside YPSW-1, for three they work with YPSW-2, and for two they work with YPSW-3, then this SSW is assigned to YPSW-1.⁵ If YPSW-1 is then randomly allocated to the intervention group, this SSW will also be assigned to the intervention group (and vice versa). Note that two or more SSWs might be assigned to a single YPSW under this model. The aim in doing this assigning is to generate a set of YPSW/SSW ‘clusters’ that between them cover as many eligible YP as possible. The randomisation steps are described in detail in the Appendix.

The steps in the randomisation are summarised below:

Step 1	Assign each SSW to a unique YPSW (the one they work with for most YP)
Step 2	Randomly allocate YPSW to either intervention and control
Step 3	Assign each SSW to ‘intervention’ or ‘control’ with the allocation being the same as the allocation to group of their ‘unique YPSW’
Step 4	Having determined the group status for every YPSW and SSW, establish which of four arms each YP now belongs to:

⁵ With assignment to an SSW being done randomly if there are two or more SSWs with which they share the same number of families.

	
Arm 1 : Both of the YP's SSW and YPSW assigned to intervention;
 
Arm 2 : Both of the YP's SSW and YPSW assigned to control;
 
Arm 3: The YP's SSW assigned to intervention but their YPSW assigned to control
 
Arm 4: The YP's SSW assigned to control but their YPSW assigned to intervention.
 
Only those in Arms 1 and 2 are used in the primary analysis.

--	---

This approach to randomisation does not give a four-arm RCT with balance across all four arms. Analysis Arms 1 and 2 will be balanced (which is vital for the primary analysis), and Arms 3 and 4 will be balanced, but the YP in Arms 3 and 4 will have different experiences to those in Arms 1 and 2 in the sense that the Arms 3 and 4 YP will be more likely to have a YPSW and SSW who work together infrequently. This does not affect the primary analysis, which compares just Arms 1 and 2, but in the exploratory analysis that compares all four arms the lack of balance will be acknowledged.

Once randomisation has been completed, each young person will have been assigned to one of the four randomisation arms. Some contamination during the trial is inevitable (with some 'control' YP being assigned to a trained social worker during the trial and vice versa). This will be monitored and sensitivity analysis will be conducted to establish the degree to which this dilutes the overall effect sizes (see analysis section).

Sample size calculations overview

Our primary analysis (which uses externalising behaviour as measured through the SDQ as an outcome) focuses on the YP where both the YPSW and SSW have either been assigned to the intervention group or to the control group (Analysis Arms 1 and 2 as described in the randomisation section above). Arms 1 and 2 between them cover 66% of all the eligible YP identified as in-scope for the trial.

Table 2 sets out the MDES and sample sizes that were originally anticipated and as they were presented in version 1 of the trial protocol. The final column sets out our revised estimates after recruitment of LAs, baseline data collection, and randomisation. The original intention was to recruit 10 LAs to the trial rather than the eight achieved, and the initial predictions of response rate at baseline proved too optimistic. However, the number of social workers was much larger than anticipated, which reduces the average cluster size. Nevertheless, the MDES

has increased from the initial protocol estimate of 0.21 standard deviations to 0.24 standard deviations.

The assumptions behind the calculations are:

- Across the eight LAs, the total number of eligible YP is 1,477. Of these, 979 have been assigned to one of the two primary analysis arms: 458 to the group where both the YPSW and the SSW are assigned to the intervention group and 521 to the group where both the YPSW and the SSW are assigned to the control group.

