The analysis of the efficacy trial data will be on an intention-to-treat basis. Estimates of impact per outcome will be based on a multilevel linear regression model with two levels, YPSW and YP, with the baseline version of each outcome being entered as a covariate. LA will be entered as a fixed effect. The analysis will be conducted in SPSS v28.0.1.1 via the MIXED procedure.

If, after non-response, we have data that is essentially unclustered then a single-level model will be fitted.

Primary outcome analysis

The primary outcome measure for YP in the trial is the SDQ externalising score.

The SDQ questionnaire includes five subscales, each with five items, that measure: 1. Emotional symptoms; 2. Conduct problems; 3. Hyperactivity/inattention; 4. Peer problems; 5. Prosocial behaviour. FCs score from 0 to 2 on each item using a scale 'not true', 'somewhat true' or 'certainly true', thus producing a score for each subscale from 0 to 10, where a lower total score is a better outcome for subscales 1-4, and the reverse for subscale 5 (prosocial behaviour). The 'externalising' score (from 0 to 20), is generated by summing the scores of the conduct and hyperactivity subscales.

The calculation of the externalising score will follow the standard SDQ scoring rules. The score will only be calculated where both subscales have a valid score (that is, at least three of the five items have been answered), others being set to missing. Each subscale will be calculated as (total subscale score)*5/(number answered).

The main regression model specification is as follows:

$$Y_{ijk} = \beta_0 + \beta_1 \text{Group}_{jk} + \beta_2 X_{ijk} + \beta_3 LA_k + u_{ijk} + \varepsilon_{ijk} \quad (\text{Eq 1})$$

where

Y_{ijk} = externalising score at follow-up for young person i belonging to assigned at baseline to YPSW j within LA k;

$\beta_0, \beta_1, \beta_2, \beta_3$ = fixed effect parameters;

Group_{jk} = indicator variable for group allocation of the YP's YPSW and SSW (0=control; 1=intervention) within LA k;

X_{ijk} = baseline externalising score for young person i assigned at baseline to YPSW j within LA k;

LA_k = a vector for the local authority dummy variables, of which there will be seven. β_3 is a coefficient vector for the LA dummy covariates;

u_{ij} =random effect for i th member of YPSW j ;

ε_{ijk} = residual error term for i th member of cluster j .

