If, at the analysis stage, the average cluster size proves to be very close to one (that is 1.1 or below) we will use a single-level model rather than two-level. In this case the model will be:

$$Y_{ik} = \beta_0 + \beta_1 Group_{ik} + \beta_2 X_{ik} + \beta_3 LA_k + \varepsilon_{ik} \quad (\text{Eq 2})$$

where

Y_{ik} =externalising score at follow-up for young person i within LA k ;

$\beta_0, \beta_1, \beta_2, \beta_3$ = fixed effect parameters;

$Group_{ik}$ = indicator variable for group allocation of the YP's YPSW and SSW (0=control; 1=intervention) within LA k ;

X_{ik} = baseline externalising score for young person i within LA k ;

LA_k = a vector for the local authority dummy variables, of which there will be seven. β_3 is a coefficient vector for the LA dummy covariates;

ε_{ik} = residual error term.

Secondary outcome analysis

There are a range of secondary outcome measures reflecting the fact that the Theory of Change suggests that impacts should be observed for all the groups potentially affected by the SW training, namely YP, FCs, and the social workers themselves.

1. Young people

There are six secondary outcomes for YP:

- The SDQ internalising score (continuous variable);
- The SDQ prosocial score (continuous variable);

and four outcomes taken from SSSA903 data:

- One or more unplanned moves (binary);

- Transition into residential care (binary);
- Conviction or subject to youth caution (binary);
- Any missing from care episodes (binary).

2. Foster carers

There are four secondary outcomes for foster carers (detailed in the trial protocol):

- The three Professional Quality of Life (ProQOL) subscales (continuous variables):
 - o compassion satisfaction;
 - o burnout;
 - o secondary traumatic stress.
- Knowledge and understanding of TIP score (continuous).

3. Social workers

For social workers in the trial, there is just one secondary outcome:

- ARTIC score (continuous)

The analysis of the secondary outcomes will be conducted following similar overall model specifications as the primary outcome analysis, but with some modifications to reflect the nature of the data. These are:

- The models for the binary outcomes will be logistic regressions rather than linear;
- For the SSDA903 outcomes, for YP just entering foster care there will be no applicable baseline data. To account for this, a baseline outcome will be included in the model coded as categorical: present, absent; not applicable.

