The characteristics shown will be: YP randomised per LA, gender, age, ethnic group, SDQ externalising mean at baseline, and SDQ internalising and prosocial score means at baseline.

Missing data

We will describe and summarise the extent of missing data per outcome, and the reasons for data being missing where known will be reported on. We will document how much missing data is unit non-response and how much is item non-response, and whether there is evidence for trial imbalance because of missing data either at baseline or follow-up.

The primary ITT regression analysis will be based on complete cases, that is those for which all of the variables needed for the model are complete. The implicit assumption here is that missing data at follow-up is 'missing completely at random' (MCAR). However, because the rate of missing data in this trial is inevitably high (because of non-response to the surveys by FCs either at baseline or follow-up), we will assess the sensitivity of the results to alternative assumptions about the mechanisms leading to missing data.

¹¹ We ruled out analysis that tries to control for these switches because we will not have rich enough data to know when during the trial period the switch occurred, and because of the additional complexity introduced because both or just one of the professionals could be switched

Firstly, we will use the baseline outcome variables for YP and FCs¹², together with other YP and FC characteristics to model (via a logistic regression) the probability per YP of a case being in the intervention arm rather than the control arm. This will identify any observable predictors of imbalance, and the regression model (Eq 1) will be re-run to include, as covariates, any significant predictors that are identified from this logistic regression. This will help establish whether the effect sizes are influenced by the level and nature of missing data, under an assumption of missing at random (MAR).

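### Young people who leave foster care are excluded after randomisation from all but the move outcomes, including conviction/caution and missing-from-care, under an intention-to-treat label

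*SAP*

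**What the plan says.** **The exclusion.** Design overview, Data collection: "If a YP moves out of foster care entirely they will be excluded from the trial analysis". A single carve-out is attached to this rule, worded as "the exception being the secondary outcomes that capture moves". The sample size section agrees: it treats still being in foster care as part of eligibility at follow-up, within a single 70% figure that also covers questionnaire completion.

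**The label.** Analysis, Primary outcome analysis: "The analysis of the efficacy trial data will be on an intention-to-treat basis". Missing data: "The primary ITT regression analysis will be based on complete cases".

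**The outcomes.** RQ2 in the Introduction asks for the effect of training on placement stability, using "SSDA903 data¹ on reasons for moves (those categorised as ‘unplanned’) and transitions into residential care". Four binary YP outcomes come from the SSDA903: unplanned moves, transition into residential care, conviction or caution, and missing-from-care episodes. Only the first two capture moves. On completeness the SAP says: "We expect to have close to complete data on these outcomes for all YP who stay in foster care".

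**The concern.** Whether a YP is still in foster care at follow-up is known only after randomisation, and RQ2 asks whether the training changes part of it. Dropping leavers therefore compares arms on a subset that the intervention may have shaped. If training keeps some of the more troubled YP in placement, the intervention arm keeps them in its analysis set while the control arm loses their counterparts. Success on RQ2 could then make the training look worse on externalising behaviour, convictions and missing episodes.

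The problem is sharpest for conviction/caution and missing-from-care. The SSDA903 is the return on looked-after children. It has to show a move into residential care, since that is an outcome, and it also supplies these two outcomes. A YP who moves to residential care can thus have recorded events, even ones before the move, that the analysis discards.

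**Working it through.** **1. The plan's own figures.** 979 × 0.57 = 558 and 558 × 0.70 = 391, split 183 and 208. With the SAP formula, ICC 0.2, cluster size 1.5 and correlation 0.6:

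2.8 × √[(1/183 + 1/208) × (1 + 0.5 × 0.2) × (1 − 0.36)] = 0.238 sd.

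The stated 0.24 reproduces, and the implied standard error is 0.238/2.8 = 0.085 sd. The sample-size arithmetic is not at fault. The 70% merges leaving with non-response, so the number of leavers cannot be read from the SAP and every leaving rate below is an assumption.

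**2. Externalising score.** Scores were simulated with a true effect of zero, a baseline/follow-up correlation of 0.6 and adjustment for baseline as in Eq 1. Higher scores are worse, so a positive value counts against the training.

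| Leaving, control vs intervention | Assumed link between leaving and score | Bias (sd) | Share of 0.24 |
|---|---|---|---|
| 10% vs 10% | correlation 0.3 to 0.5 with follow-up score | about 0 | about 0 |
| 10% vs 6% | control leavers 0.8 sd worse | about 0.012 to 0.019 | 5% to 8% |
| 15% vs 10% | correlation 0.3 to 0.5 with follow-up score | 0.015 to 0.029 | 6% to 12% |
| 20% vs 10% | correlation 0.3 to 0.5 with follow-up score | 0.028 to 0.053 | 12% to 22% |

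In the 10% vs 6% row, the lower values arise when leaving depends equally on the baseline and follow-up scores, because the covariate then removes more of the difference.

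**3. Conviction/caution.** Assume no true effect on conviction, a 4% risk in YP who would stay under either allocation and 15% in the rest, and 20% versus 10% leaving, with everyone who would leave under intervention also leaving under control.

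- All YP, either arm: 0.80 × 0.04 + 0.20 × 0.15 = 6.2%.
- Control stayers: 4.0%.
- Intervention stayers: (0.80 × 0.04 + 0.10 × 0.15)/0.90 = 5.2%.
- Stayers-only odds ratio: (0.0522/0.9478)/(0.04/0.96) = 1.32, where the truth is 1.
- Share of control events discarded: 1 − 0.032/0.062 = 48%, that is 521 × 0.062 = 32.3 expected events cut to 521 × 0.032 = 16.7.

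With 15% versus 10% leaving, the odds ratio is 1.16 and 40% of control events are lost. If the risk is 20% in YP whom the training keeps in placement and 25% in those who leave regardless, the odds ratios are 1.23 (15% vs 10%) and 1.47 (20% vs 10%), with 51% and 58% of control events lost.

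**4. Sample available for the SSDA903 outcomes.** With all 458 + 521 YP, no baseline correlation and cluster size 1 to 1.5, the same formula gives 0.18 to 0.19 sd, slightly better than the 0.20 sd that the SAP expects. With 80% of them it gives 0.20 to 0.21 sd.

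**5. Does another section put leavers back?** The Missing data section offers complete cases, a covariate-adjusted rerun, a comparison of SSDA903 SDQ scores for respondents and non-respondents, and extreme-value bounds if data appear to be missing not at random. None of these mentions leavers, who are defined as excluded rather than as missing.

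**The case against.** Several points on the other side stand.

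- No sentence names conviction or missing-from-care as restricted to stayers. That follows from the exception clause, which sits in a paragraph mainly about surveys. The expectation of near-complete data for stayers cannot settle it: it covers all four SSDA903 outcomes, one of which cannot be analysed in stayers alone, and it concerns availability rather than the analysis set. The sample size section also expects smaller losses for these outcomes. The authors may intend to keep leavers, but the text as written removes them.
- A reader might infer that leaving as such is an outcome the training is meant to change. The SAP supports this only for residential care and for unplanned moves that end foster care. Other exits are not named outcomes.
- A reader might size the bias without the baseline covariate: with leavers 0.8 sd above the arm mean, 0.8 × (0.10/0.90 − 0.06/0.94) = 0.038 sd, about one sixth of 0.24. Eq 1 adjusts for baseline, and under those leaving rates about 0.01 to 0.02 sd remains.
- RQ1 concerns YP in family settings and the SDQ is carer-reported, so after exit there may be no carer to respond. For the SDQ the defect is therefore mainly one of estimand, label and accounting for leavers.
- A reader might conclude that multiple imputation from the SSDA903 SDQ is required. That SDQ is a total score, excludes YP over 16 and those looked after for under 12 months, and varies in timing (Missing data and its footnote 13). Imputation is a debatable choice here.
- Some safeguards exist: residential transitions are compared by arm, baseline balance is shown among those with follow-up, and known reasons for missing data are reported. They would reveal part of the problem but would not restore discarded events.

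**Conclusion.** The point holds. As written, the plan makes a post-randomisation exclusion that covers two administrative outcomes whose data should be held for YP who move into residential care, and it calls the result intention-to-treat. The documents do not show that the trial will be biased: with equal and equally selective leaving the bias is about zero. If training reduces leaving and leavers have worse outcomes, it runs against the training.

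For the primary outcome the likely size is modest: 0.01 to 0.02 sd is roughly 0.1 to 0.2 of the 0.085 sd standard error, and 0.05 sd is about 0.6 of it. For conviction/caution the assumed scenarios give spurious odds ratios of about 1.2 to 1.5 and lose 40% to 58% of control events, which is the stronger reason to change the plan. All these sizes rest on assumed leaving rates and risks.

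**What to change.** **SSDA903 outcomes.** State that all four are analysed in all Arm 1 and 2 YP (979) who have SSDA903 data, whatever their placement at follow-up. Count events recorded before any exit from care, and state the rule for YP who leave care altogether.

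**SDQ outcomes.** Describe the estimates as applying to YP still in foster care, not as unqualified intention-to-treat. Report leavers by arm and reason, separately from non-response, and include them explicitly in the sensitivity analyses of the Missing data section. Say whether a move to supported lodgings counts as leaving, since that setting is part of the target group.

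**Cost.** SAP wording and a little extra analysis, with no new data collection. The remaining weakness is that YP who leave care altogether have incomplete SSDA903 follow-up, and no choice of analysis set removes that. The rule should be fixed before outcomes are analysed, because the statistician who randomises also analyses and is not blind to allocation.
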